| Study Period | Screen | Treatment period | | | | | | | | EOT | FUV | OP |
|---|-----------|------------------|-----------------|--------------|--------------|-----------------|--------------|--------------|-------------------------|------------------------|--------------------------|---------------------------------|
| Visit | 1 | 2 | 3 | 4 | 5 | 6 | 7 | 8 | 9 to 26 | EOT | FUV | OP1 etc |
| Weeks after randomization | -2 | 0 | 1 | 2 | 3 | 4 | 5 | 6 | 7 to 24 | | | |
| Day ¹ | -14 to -1 | 1 | 8 (+/-2) | 15 (+/-2) | 22 (+/-2) | 29 (+/-2) | 36 (+/-2) | 43 (+/-2) | Repeat visits 3 to 8 | 0-7 after last dose | +28 (+7) after EOT | Every 4 weeks (+/-7 days) |
| Vital status ¹⁹ | | | | | | | | | | | | X |
| Blood sampling for pharmacokinetic analysis | | | X ²⁰ | | | X ²¹ | | | | | | |

Screen **Screening visit:** is performed within 14 days prior to first drug administration.

Treatment period Patients may continue on treatment for unlimited visits, until the criteria for stopping medication are met (see [Section 3.3.4](#)). Visits 3-8 are repeated when a patient continues beyond Visit 8. After week 24, the visits should follow the next Flow Chart table.

EOT **End of treatment:** EOT visit is done within 7 days after last drug administration.

If a patient permanently discontinues study treatment at a scheduled visit, the EOT visit should be performed instead of this visit.

FUV **Follow-up visit:** all patients should have a follow-up visit 28 days (+7days) after the EOT visit.

OP **Observational Period:** All patients will be followed-up for overall survival at 4 week intervals after the last follow-up for progression visit until death, withdraw of consent, lost to follow-up or completion of the whole trial whatever occurs earlier. See [section 5.2.2.2](#). After database lock for primary analysis, frequency will be every 3 months.

- 1) Recommended day for visit.
- 2) Written informed consent must be obtained before any study-specific screening assessments are performed.
- 3) In case progression is detected, this should be confirmed by imaging within 14 days.
- 4) Tumour imaging should include CT scans or MRI of the head and neck, chest, upper abdomen to include the liver, and if clinically indicated, imaging of any other known or suspected sites of disease. The same radiographic procedure must be used throughout the study, and imaging guidelines must be followed. Imaging will be performed until progression at the following time points:

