2. RATIONALE, OBJECTIVES, AND BENEFIT - RISK ASSESSMENT

2.1 RATIONALE FOR PERFORMING THE TRIAL

Patients with HNSCC progressing after having received standard platinum-based therapy for R/M disease are left with few opportunities for treatment, and median life expectancy is estimated to be approximately six months ([R10-5848](#), [R11-0801](#), [R10-5936](#)).

The tyrosine kinase EGFR has been implicated in supporting oncogenesis and progression of human solid tumours, and the receptor has been the target for recently developed molecules. The introduction of the EGFR inhibiting antibody cetuximab has improved the survival when added to platinum based therapy in patients with previously untreated R/M HNSCC as compared to chemotherapy alone ([R10-5937](#)). As a single agent, cetuximab has also showed activity in patients with platinum-refractory HNSCC, although no survival benefit was shown ([R08-1660](#)). However, cetuximab has not been assessed in comparison with other agents or with best supportive care in patients with previously treated R/M HNSCC. Small molecule inhibitors, such as gefitinib, have been explored, however when compared to methotrexate in the R/M setting, no survival benefit has yet been shown ([R10-5936](#)). Methotrexate or taxanes are frequently used in routine clinical practice after platinum failure, although no phase III trials have formally demonstrated that these chemotherapeutics increase survival. Cetuximab is still the only targeted agent approved (by FDA) in this setting and the approval was achieved based on a response rate of 13% from a single-arm Phase II study ([R08-1660](#)). Recently the immunotherapy agents pembrolizumab and nivolumab have been approved (by FDA) for the treatment of patients with R/M HNSCC with disease progression on or after platinum containing chemotherapy (see [Section 1.1.2](#)). Despite the emergence of new agents, it is evident that most patients do not respond to treatment and that there is still a high unmet medical need in second-line R/M HNSCC.

Afatinib is a second generation irreversible EGFR-TKI. Proof of concept of Afatinib in R/M HNSCC has been established in a BI phase II study of Afatinib versus cetuximab, where the anti-tumour activity of Afatinib was at least comparable to the activity of cetuximab ([P10-12525](#)).

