All patients will visit the investigational site weekly for assessment of safety parameters and AEs. Tumour response will be assessed regularly by CT scan/MRI (see [Flow Chart](#)) until progression. At disease progression, confirmed by tumour imaging, patients will be discontinued from the study medication.

The end of treatment (EOT) is defined as permanent discontinuation of Afatinib or methotrexate. Related EOT information needs to be obtained. Patients who permanently discontinue the study medication for any other reason than progression of disease (or withdrawal of consent) should continue the scheduled tumour imaging visits until progression as described in [Section 6.2.3](#). The requirement to continue imaging for study purposes for such patients will be removed following the database lock for primary analysis.

Following the EOT visit, patients should come to a follow-up visit (FUV) and then continue in the observational period. During the observational period, data of survival (vital status), related SAEs/AESIs and concomitant anti-cancer therapy will be collected. For patients who progressed on treatment, the observation period for overall survival starts after the FUV (end of residual effect) visit. For patients who have not progressed on treatment, this period starts after the last additional FU visit. A patient is considered to have completed the trial following death, withdrawal of consent or lost to follow-up.

Primary statistical analyses will be performed when the required number of progression free survival events has occurred as described in [Section 7.6](#). The clinical trial report will be written based on primary analysis results. An addendum to the clinical trial report may be used to summarise data collected beyond database lock for the primary analysis.

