Although there is no world-wide accepted standard treatment for R/M HNSCC patients failed to the first line chemotherapy, they often receive several sequential anti-cancer treatments. It is expected that the trial medication will not be the last anti-cancer treatment of study subjects. The subsequent treatment(s) may impact on the survival. This situation was observed in the IMEX and ZALUTE trials ([R10-5936](#), [R11-0801](#)) where 30-40% and 20-30% subjects of respective study received subsequent anti-cancer therapies. Therefore, PFS is selected as the primary endpoint in order to assess the efficacy of the trial medications as accurate as possible.

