4.2.2 Restrictions

4.2.2.1 Restrictions regarding concomitant treatment

Additional experimental treatment is not allowed concomitantly with the administration of study medication, nor any additional anti-cancer therapy between four weeks prior to randomization and until EOT (with the exception of megestrol acetate and palliative short-course radiotherapy to bone lesions for pain relief).

Afatinib is a substrate of the P-glycoprotein (P-gp) transporter. Caution should be exercised when combining Afatinib with P-gp modulators ([U03-3218](#)). For a list of potent P-gp inhibitors and inducers (see [Appendix 10.5](#)). Patients treated with methotrexate should not receive any of the prohibited medications as listed in the current SPC/PI for methotrexate therapy.

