5.3.2.2 Concomitant therapies and diagnoses

Concomitant diagnoses and/or therapies present during trial participation (between the screening visit and at least until 28 days after the last administration of study medication) will be recorded in the eCRF. In case of medical or surgical procedures that would affect the assessment of the radiology findings, the investigator has to describe the type and location of intervention as well as the results from biopsy or cytology assessment in the eCRF.

Any anti-cancer therapy (including radiotherapy) administered after EOT and throughout the observational period, will be recorded in the eCRF with the same information as mentioned in [Section 5.3.2.1](#).

Proprietary confidential information. © 2019 Boehringer Ingelheim International GmbH or one or more of its affiliated companies

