6. GENERAL ANALYSIS DEFINITIONS

6.1 TREATMENT

In the clinical trial report, all randomized patients will be classified into either ‘Afatinib 40’ or ‘MTX 40’. For efficacy analyses, patients will be analysed as randomised. For safety analyses, patients will be analysed as treated, according to the initial treatment taken.

Even though this trial is open-label, according to BI SOP [1], report planning will be done in a ‘blinded’ manner. Therefore, before database lock, all patients will be randomly assigned a dummy treatment code, DummyRed or DummyBlue, and displayed as such in all programmed tables, listings and figures (TLFs).

For safety reporting purpose, the following treatment periods are defined:

- Screening: from informed consent to the date of first dose of study medication
- On-treatment: date of first dose of study medication to last dose
- Post-treatment: date of last dose + 1 day to the 28th day after last dose
- Post-study: from 29th day after last dose onwards

In summarizing the safety data, all adverse events with onset date during the on- and post-treatment periods will be considered as ‘treatment-emergent’. Refer to [Section 7.8.1](#) for more details.

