7.8.1 Adverse events

Unless otherwise specified, the analyses of adverse events (AEs) will be descriptive in nature. All analyses of AEs will be based on the number of patients with AEs and NOT on the number of AEs.

Furthermore, for analysis of AE attributes such as duration, severity, etc, multiple AE occurrences collected on the CRF will be collapsed into AE episodes provided that all of the following applies:

- The same MedDRA lowest level term was reported for the occurrences
- The occurrences were time-overlapping or time-adjacent (time-adjacent if the second occurrence started on the same day or on the day after the end of the first occurrence)
- Treatment did not change between the onset of the occurrences OR treatment changed between the onset of the occurrences, but no deterioration was observed for the later occurrence

For further details on summarization of AE data, please refer to the guideline 'Handling and summarization of adverse event data for clinical trial reports and integrated summaries' [9].

The analysis of adverse events will be based on treatment-emergent adverse events, i.e. all adverse events with an onset date between first drug intake and 28 days after last drug intake. All adverse events occurring before first drug intake will be assigned to 'screening' and all adverse events occurring after last drug intake + 28 days will be assigned to 'post-study'. For details on the treatment definition, see [Section 6.1](#).

An overall summary of adverse events will be presented. This summary will exclude the rows 'Severe AEs', and 'Other significant AEs' but will include additional rows for 'AEs leading to dose reduction', 'AEs leading to permanent discontinuation of study drug', and 'AEs by highest CTCAE grade'.

The frequency of patients with adverse events will be summarised by treatment, primary system organ class (SOC) and preferred term (PT) of MedDRA (using the version that is current at the time of analysis). All tables will be sorted by SOC according to the standard sort order specified by the European Agency for the Evaluation of Medicinal Products (EMEA); PTs will be sorted by frequency (within SOC). Frequency tables will be created for the following events:

- All AEs
- Drug-related AEs
- AEs leading to dose reduction
- AEs leading to treatment discontinuation
- Drug-related AEs leading to treatment discontinuation
- Serious AEs
- Drug-related serious AEs
- Fatal AEs

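### The SAP's 28-day adverse-event window runs on after a new anti-cancer therapy may start, and no visible rule ends or flags it there

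*Protocol*

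**What the plan says.** **When other therapy may begin.** Protocol 4.2.2.1 permits no further experimental treatment with study medication, "nor any additional anti-cancer therapy between four weeks prior to randomization and until EOT", apart from megestrol acetate and short palliative radiotherapy to bone. Protocol 3.1 fixes the end point of that bar: "The end of treatment (EOT) is defined as permanent discontinuation of Afatinib or methotrexate". The Flow Chart notes add that the "EOT visit is done within 7 days after last drug administration". Protocol 6.2.3.1 leaves later treatment to the investigator and the patient and states no minimum gap. In SAP Table 6.2: 1, code D1 makes other anti-cancer therapy a violation only if it is used before study drug is stopped.

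**Which adverse events are counted.** SAP 6.1 defines a period after treatment, "Post-treatment: date of last dose + 1 day to the 28th day after last dose". Events with onset in that period or on treatment are treatment-emergent, and patients are classified by the study treatment they first took. SAP 7.8.1 uses the same span: "all adverse events with an onset date between first drug intake and 28 days after last drug intake". Protocol 5.2.2.2 gives 28 days as the residual effect period of both drugs.

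**What is known about further therapy.** Of two earlier trials, Protocol 3.2 says that "30-40% and 20-30% subjects of respective study received subsequent anti-cancer therapies". Protocol 5.3.2.2 provides that "Any anti-cancer therapy (including radiotherapy) administered after EOT and throughout the observational period, will be recorded in the eCRF".

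**The concern.** The two time limits do not meet. The bar on other therapy ends when study drug stops, or at a visit within a week of that. The adverse-event window closes 28 days after the last dose. A patient who moves promptly to another cancer drug spends the rest of the window exposed to it, and events that it causes are tabulated under the study arm.

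The SAP deals with new therapy elsewhere. PFS is censored at it (rule 6 of SAP Table 7.4: 1). For OS, SAP 7.5.2 plans summaries of subsequent therapy and, if necessary, adjusted models. The adverse-event analysis has no counterpart, although comparing the safety of the two arms is a secondary objective (Protocol 2.2). At stake is how cleanly the all-cause, serious, fatal, special-interest and grade tables describe the two study drugs.

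**Working it through.** The plan gives no figure of its own on this point, so there is none to reproduce. The check compares the two time limits and then bounds the number of patients.

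**1. Length of the overlap**
- If the bar ends at discontinuation (Protocol 3.1): 28 − 0 = 28 days.
- If it ends at the EOT visit, at most 7 days after the last dose (Flow Chart notes): 28 − 7 = 21 days.
- Up to 21-28 days per patient can therefore fall under another therapy.

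**2. Tables affected**
- Open to such events: all adverse events, serious, fatal, special-interest, and the breakdown by highest CTCAE grade (SAP 7.8.1).
- Partly protected: the drug-related tables, which rest on the investigator's yes/no causality judgement (Protocol 5.2.2.1.4) in a trial without blinding (Protocol 4.1.5.1).
- Essentially unaffected: events leading to dose reduction or discontinuation, which concern action taken with study drug.
- Laboratory tables: SAP 7.8.2 uses the same 28-day span. After EOT, the only scheduled safety sample is at the follow-up visit, 28 (+7) days after an EOT visit held 0-7 days after the last dose. That is 0 + 28 = 28 to 7 + 35 = 42 days after the last dose, almost entirely outside the window.

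**3. Ceiling on patients affected**

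Inputs: 20-40% with subsequent therapy at any time (Protocol 3.2, two other trials) and planned arms of 220 and 110 (Protocol synopsis). The ceiling assumes that every such patient starts immediately after the last dose.
- Afatinib: 0.20 × 220 = 44 to 0.40 × 220 = 88.
- Methotrexate: 0.20 × 110 = 22 to 0.40 × 110 = 44.

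**4. Illustrative share of the window**

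Assumption: time on treatment is exponential with the protocol's PFS medians (3.0 and 2.1 months, 30.4375 days per month). Mean = median / ln 2; tail share = 28 / (28 + mean).

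| | Afatinib | Methotrexate |
|---|---|---|
| Mean days on treatment | 3.0 × 30.4375 / 0.693 = 131.7 | 2.1 × 30.4375 / 0.693 = 92.2 |
| 28-day tail as share of window | 28 / 159.7 = 17.5% | 28 / 120.2 = 23.3% |
| Window time on next therapy if 20-40% start at once | 3.5-7.0% | 4.7-9.3% |

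The last row is a worst case given the 20-40%, because not all such patients start within 28 days.

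**The case against.** The strongest reply is that the window is right as it stands. Twenty-eight days is the stated residual effect period of both drugs, treatment-emergent is a label of timing and not of cause, and the safety analysis is declared descriptive and exploratory (Protocol 7.3.3). SAP 7.8.1 has separate drug-related tables, and Protocol 5.2.2.1.4 tells investigators to weigh concomitant medication when judging cause. SAP 7.8.1 also defers further detail to a sponsor guideline on adverse-event summaries (SAP reference 9), which may contain a truncation rule. All of this stands. It makes the point a missing sensitivity analysis, not an error in the window. It does not fill the gap in the all-cause, serious, fatal and grade tables, which no causality judgement filters.

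A reader might also infer more than the documents support:
- **That the next therapy's toxicity is reported as study-drug toxicity.** It is tabulated under the arm by timing. Attribution has its own tables.
- **That afatinib patients mostly move to methotrexate or a taxane, so the arms' profiles converge.** Protocol 2.1 says "Methotrexate or taxanes are frequently used in routine clinical practice after platinum failure", which describes practice after platinum, not after study drug. No section names the agents used next in either arm. If methotrexate patients also go on to a cytotoxic drug, the arms could move in parallel or apart.
- **That several percentage points are added to event rates.** Assuming that 25-75% of the 20-40% start within 28 days, and that 5-20% of those have a given event, the result is 0.20 × 0.25 × 0.05 = 0.25 points to 0.40 × 0.75 × 0.20 = 6 points. The last two ranges come from no document, and the result spans a factor of 24.
- **That the laboratory tables are equally exposed.** Only unscheduled samples, or a follow-up visit at its earliest possible date, could fall in the window.

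**Conclusion.** The gap is real and affects both arms. Other therapy is barred only until EOT, the adverse-event window runs 28 days past the last dose, and no visible rule truncates or flags it when a new therapy starts. Events of a next therapy begun in those 21-28 days can therefore enter the all-cause, serious, fatal, special-interest and grade tables under the study arm.

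The size cannot be derived. The ceiling of 44-88 afatinib and 22-44 methotrexate patients rests on two assumptions: that the 20-40% from two other trials carries over to this one, and that every such patient starts at once. The documents do not give the share starting within 28 days, the agents used or the direction of any distortion. The window-time illustration also assumes that time on treatment follows the assumed PFS. The conclusion holds unless the cited sponsor guideline already contains a cut-off. This is a cheap improvement to the safety reporting. It does not make the planned tables wrong.

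**What to change.** Keep the 28-day tables as the main set. In SAP 7.8.1, add a sensitivity repeat of the adverse-event overview and of the grade 3 or higher, serious, fatal and special-interest tables. It should count only events with onset before the earlier of last dose + 28 days and the start of the first new systemic anti-cancer therapy. Report it alongside the main set, with the number of patients per arm whose window was cut, which would supply the share that is now unknown. If the sponsor guideline already has such a rule, a cross-reference is enough. The laboratory tables need no repeat.

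The cost is a paragraph in the SAP and a second run of programmed tables. Start dates of later therapy are already collected (Protocol 5.3.2.2 and 6.2.3.3), so no data, visit or treatment rule changes.

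The downside is that some true late study-drug events in patients who switch drop out of the repeat. Observation is also shortened only in those patients, and switching may differ by arm. The truncated set should therefore not replace the main tables as the basis for comparing the arms.

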4.2.2.2 Restrictions on diet and life style

For Afatinib: Patients should be advised to avoid lactose-containing products or any foods known to aggravate diarrhoea, see [Section 4.2.3.1](#).

To prevent skin related adverse events intense irradiation with UV light should be avoided, see also [Section 4.2.3.2](#).

For methotrexate: Compare SPC/PI.

4.2.3 Management of expected adverse events

Dermatologic AEs and diarrhoea are the most common side effects associated with treatment with Afatinib. Treatment of these side-effects should be proactive e.g. should be started as early as possible after onset of symptoms, and side effect management material will be given out to patients. Recommendations for management are described below. For dose modifications of Afatinib, see [Section 4.1.4.1](#).

The most common undesirable effects of methotrexate treatment are ulcerative stomatitis, leukopenia, nausea, and abdominal discomfort. For further information, see the SPC/PI. For dose modifications of methotrexate, see [Section 4.1.4.2](#).

4.2.3.1 Management of diarrhoea following treatment with Afatinib

Diarrhoea occurs at a high frequency and generally begins within two weeks of exposure to Afatinib. Although usually mild to moderate, diarrhoea may compel treatment modification or discontinuation, so early management is essential (see [Table 4.2.3.1: 1](#)). At the time of Afatinib initiation, patients should be given anti-diarrhoeal agents (such as loperamide). Investigator should ask patients to keep anti-diarrhoeal agents with them at all times, and instruct the

Proprietary confidential information. © 2019 Boehringer Ingelheim International GmbH or one or more of its affiliated companies

appropriate use. Patients should also be advised to drink adequate an amount of fluids during diarrhoea. For the use of anti-diarrhoeal medication, please refer to local SPC/PI.

Table 4.2.3.1: 1 Grade specific treatment of Afatinib related diarrhoea

| Severity (CTCAE grade) | Description | Intervention concerning Afatinib dose | Specific intervention |
|----------------------------|---|---|---|
| Mild (grade 1) | 
 Increase of <4 stools per day over baseline Mild increase in ostomy output compared with baseline | Continue same dose | 
 Stop laxatives and advise patient to drink sufficient water or clear fluids per day 4 mg (2 tablets) of loperamide to be taken immediately, followed by 2 mg (1 tablet) after each loose stool until bowel movements cease for 12 hours |
| Moderate (grade 2) | 
 Increase of 4-6 stools per day over baseline i.v. fluids indicated <24 hours Moderate increase in ostomy output compared with baseline; Not interfering with activity of daily life (ADL) | Continue same dose unless grade 2 diarrhoea continues for ≥2 days (48 hours) in which case treatment must be interrupted until recovered to grade ≤1 followed by dose reduction | 
 Continue loperamide Assess for dehydration and electrolyte imbalance Consider i.v. fluids and electrolyte replacement |
| Severe (grade 3) | 
 Increase of ≥7 stools per day over baseline Incontinence i.v. fluids >24 hours Hospitalisation Severe increase in ostomy output compared with baseline Interfering with ADL | Dose interruption until recovered to grade ≤1 followed by dose reduction ¹ | 
 See grade 2, plus: An infectious process should be ruled out with stool cultures Aggressive i.v. fluid replacement ≥24 hours Hospitalisation to monitor progress Consider prophylactic antibiotics if patient is also neutropenic |
| Life threatening (grade 4) | 
 Life-threatening consequences (e.g. haemodynamic collapse) | Dose interruption until recovered to grade ≤1 followed by dose reduction ¹ | 
 See grade 3 |

- If despite optimal supportive care and a treatment interruption, diarrhoea does not resolve to CTCAE grade ≤1 within 14 days, treatment with Afatinib must be permanently discontinued. In the event that the patient is deriving obvious clinical benefit according to the investigator's judgement, further treatment with Afatinib will be decided in agreement between the sponsor and the investigator.

